4.2. Missing Data and Unreasonable Data

For primary efficacy and safety endpoints, if a subject withdraws from the trial prior to the 360-day follow-up or has missing data for the primary endpoint at the 360-day follow-up, Non-responder Imputation (NRI) will be applied to impute the missing values. For the primary efficacy endpoint of 360-day effective closure rate, if a subject's 360-day follow-up data is missing, that subject will be imputed as “ineffective.” For the primary safety endpoint of common complication

incidence within 360 days post-operation, if a subject's safety follow-up data within 360 days is incomplete due to lost to follow-up or other reasons, that subject will be imputed as having “experienced a common complication.”

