method = normal
nullproportion = 0.94
proportion = 0.99
sides = U
power = 0.8
alpha = 0.025
ntotal = . ;
run;↵
```

The POWER Procedure
Z Test for Binomial Proportion

Fixed Scenario Elements	
Method	Normal approximation
Number of Sides	U
Null Proportion	0.94
Alpha	0.025
Binomial Proportion	0.99
Nominal Power	0.8
Variance Estimate	Null Variance

Computed N Total	
Actual Power	N Total
0.802	121

The target and OPC of effective closure rate at 360-day post operation are set as 99% and 94%, respectively. SAS software calculation indicates that at least 121 patients are needed. Considering a dropout rate of 20%, 146 patients are required.

b) Rate of common complications during 360-day post operation

```
proc power;
onesamplefreq
test = z
method = normal
nullproportion = 0.06
proportion = 0.01
sides = L
power = 0.8
alpha = 0.025
ntotal = . ;
run; ↵
```

The POWER Procedure
Z Test for Binomial Proportion

Fixed Scenario Elements	
Method	Normal approximation
Number of Sides	L
Null Proportion	0.06
Alpha	0.025
Binomial Proportion	0.01
Nominal Power	0.8
Variance Estimate	Null Variance

Computed N Total	
Actual Power	N Total
0.802	121

The target and OPC of rate of common complications during 360-day post operation are set as 1% and 6%, respectively. SAS software calculation indicates that at least 121 patients are needed. Considering a dropout rate of 20%, 146 patients are required.

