8.3 Significance level and power

This trial adopts single-arm design and the significance level α (one-sided) = 0.025, and the power is 80%.

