8.4 Expected dropout rate

- (1) Dropout refers to the early withdrawal of the subjects during the clinical trial because of various reasons. For example, patients voluntarily withdraw the informed consent, lose follow-up and cannot complete the whole process of clinical trials due to AEs.
- (2) In the process of sample size estimation, the expected maximum dropout rate is set at 20%, which refers to the proportion of dropout cases.

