8.7.2 Missing and unreasonable data

The trial should ensure that the data records are 100% correct, especially the primary endpoints. For missing, unused and irrational data or data of withdrawal subjects, strict review should be conducted. The basic statistical principles for processing these data are as follows:

- (1) The details of each dropout subject will be described;
- (2) The last observation carried forward (LOCF) method will be applied for the missing values of the main evaluation indicators;
- (3) The missing values of qualitative or quantitative secondary endpoints are not carried forward, and are

handled according to the missing values;

- (4) The missing values of all safety endpoints are not carried forward, and are handled according to the missing values.

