10.2 Analysis of the likelihood of failure

- (1) There are too many subjects who quit the trial due to SAEs;
- (2) Subjects who lose to follow-up account for more than 20% of the sample size;
- (3) IFU and labeling information of the device cannot effectively guide the operator;
- (4) Serious safety problems are found during the trial;
- (5) Major mistakes are found in the protocol during the trial, leading to difficulty in evaluating the product efficacy;
- (6) The operation of the trial personnel is unskilled.

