4.1.1. Full Analysis Set (FAS)

Full analysis set (FAS): According to the basic principles of Intention to Treat (ITT), FAS refers to the set of subjects that comply with the ITT principles. It includes:

- a) Subjects who have been treated with the investigational device, achieved the immediate operation success, and have at least one observation data of primary endpoints after baseline;

- b) Subjects who have received treatment with the investigational device, but have failed in the implantation because of the device itself, regardless of whether there is a study device in the body.

If the implantation is abandoned due to other clinical reasons and there is no investigational device in the body, such subject will not be included in the FAS. The definition of receiving the investigational device treatment is that if any part of the device, including the occluder itself and its delivery device, contact with human body through vascular approach, it can be considered as receiving the device treatment. FAS will be the main data set for baseline data analysis, primary safety, and efficacy evaluation.

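### The SAP scores missing 360-day results in the FAS as failures where the protocol carries the last observation forward; 3 missing of 142 or 4 of 146 then rule out a pass, so 80% power with up to 20% dropout does not hold

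*SAP*

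**What the plan says.** **Protocol.** Section 8.2.1 derives 121 subjects per primary endpoint and then states: "Considering a dropout rate of 20%, 146 patients are required". Section 8.3 gives 80% power at one-sided 0.025. Section 8.4 takes 20% as the largest dropout expected, and section 10.2 lists among the possible causes of failure: "Subjects who lose to follow-up account for more than 20% of the sample size". On missing data, item (2) of section 8.7.2 says: "The last observation carried forward (LOCF) method will be applied for the missing values of the main evaluation indicators". Item (4) of the same section says: "The missing values of all safety endpoints are not carried forward". The rate of common complications is both a main indicator and a safety endpoint, so the two items conflict for it.

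**SAP.** Section 4.2 says that for both primary endpoints "Non-responder Imputation (NRI) will be applied to impute the missing values". Sections 5.1.1 and 5.1.2 repeat this for the FAS, which section 5.1 makes the primary dataset. The test is an exact two-sided 95% interval, with the lower limit above 94% for closure and the upper limit below 6% for complications. Under section 4.1.1, a successfully implanted subject is in the FAS on the condition to "have at least one observation data of primary endpoints after baseline". Section 3.1 plans 142 subjects, not 146. The SAP gives no sample size or power calculation for its own rule.

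**The concern.** Two documents in force give different rules for the primary analysis that supports registration, and neither says which prevails. Imputing failure matches neither reading of the protocol's safety rule. If the choice were settled after the 360-day data had been seen, the result would be open to challenge whichever way it went.

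The planning statements are affected as well. Adding 20% for dropout makes sense if dropouts leave the analysis and 121 evaluable subjects remain. Under the SAP, a dropout who is in the FAS stays in the denominator and is counted against the device on both endpoints. The pass rule allows only two or three failures in all, so a handful of missed 360-day visits decides the trial.

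**Working it through.** **1. The protocol's own figures.** Inputs from Protocol 8.2.1: null rate 94%, target 99% (safety: 6% and 1%), one-sided alpha 0.025, power 80%, z-test with null variance.

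n = [(1.960 × √(0.94 × 0.06) + 0.842 × √(0.99 × 0.01)) / 0.05]² = 120.65, so 121. Power at 121 is 0.802. The 146 is 121 × 1.2 = 145.2, rounded up. Both figures reproduce.

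**2. How many failures the SAP rule allows.** Let k(N) be the largest x for which the Clopper-Pearson 95% upper limit of x/N is below 6%. By symmetry this is also the largest number of non-closures with a lower limit above 94%.

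| FAS size | k: failures plus missing that still pass |
|---|---|
| 91–117 | 1 |
| 118–143 | 2 |
| 144–167 | 3 |

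Upper limits at the boundary: 3/142 gives 6.05% (fail), 3/146 gives 5.89% (pass), 4/146 gives 6.87% (fail). So 3/142 = 2.1% missing, or 4/146 = 2.7%, excludes a pass with no true failure at all.

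**3. Power per endpoint by number missing.** With c missing subjects in a FAS of N and a true failure rate of 1%, power = P(X ≤ k − c), X ~ Binomial(N − c, 0.01), and zero when c > k.

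| Missing in FAS | FAS 142 (k = 2) | FAS 146 (k = 3) |
|---|---|---|
| 0 | 82.9% | 94.0% |
| 1 | 58.8% | 82.2% |
| 2 | 24.5% | 57.7% |
| 3 | 0 | 23.8% |
| 4 | 0 | 0 |

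**4. Power per endpoint by missing rate.** With missing rate m independent of outcome, a subject counts as a failure with probability 1 − 0.99(1 − m), and power = P(X ≤ k), X ~ Binomial(N, that probability).

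| m | FAS 142 | FAS 146 |
|---|---|---|
| 1% | 46% | 67% |
| 2% | 20% | 36% |
| 5% | 0.8% | 2.3% |
| 20% | effectively 0 | effectively 0 |

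**5. Opposite verdicts on the same data.** Take a FAS of 146 in which every observed subject is closed, and 4 subjects were closed at day 180 but have no day-360 echocardiogram.

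- Protocol rule (carry forward): 146/146, lower limit 97.5%, pass.
- SAP rule (impute failure): 142/146, lower limit 93.1%, fail.

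**6. The protocol's planning pair under the SAP rule.** If 121 of 146 were evaluable and the other 25 were all in the FAS, the best attainable closure rate would be 121/146 = 82.9% (95% CI 75.8% to 88.6%), and the whole interval would lie below 94%.

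**7. Who is imputed.** Outside the FAS are subjects with no device contact, implants abandoned for other clinical reasons with no device in the body, and successful implants with no post-baseline primary-endpoint observation. Protocol 7.2.4.2 schedules echocardiography and a complication check before discharge. A successful implant assessed then and lost later is therefore in the FAS and is imputed.

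**The case against.** **The 20% is not a 360-day figure.** Protocol 7.1.5.3 and 8.4 define dropout over the whole trial, which runs to five years, and withdrawals after day 360 trigger no imputation. That is right as a definition. But section 8.2.1 applies the 20% to the 360-day sample size, so the comparison is the protocol's own. The cut-offs at 2.1% and 2.7% do not depend on it.

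**The counts assume that the FAS equals planned enrolment.** This stands as a condition. A smaller FAS gives no relief: from 118 to 143 the limit is still 2. The gap between 142 and 146 is largely a step in the exact test between 143 and 144 (power with none missing is 82.7% and 94.3%), so the size of that gap should not be put down to imputation.

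**121 of 146 is not 20% missing.** Correct: 25/146 is 17.1%. It is the pair of figures that the protocol gives, and 20% missing would be worse.

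**The protocol never claimed 80% power under failure imputation, and the rule is conservative.** Both are true. The rule cannot create a false pass, and if carry-forward became the common rule this power objection would fall away. The power statement is thus a consequence of the rule conflict, which is the main defect.

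**The SAP may be a deliberate change.** Protocol 8.8 provides a meeting procedure for modifying the SAP. The documents do not show that it was used, and 8.7.2 still states the other rule. SAP 4.1.3, 4.1.2 and 6 go some way to separating the primary safety endpoint from the observed-data safety analyses, but they do not reconcile the SAP with the protocol.

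**Conclusion.** The concern holds. The protocol and SAP prescribe different missing-data rules for both primary endpoints, the protocol contradicts itself on safety, and the difference can reverse the trial's conclusion. Under the SAP rule, 80% power per endpoint survives no missing subject at a FAS of 142 and only one (1/146 = 0.7%) at 146.

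These figures rest on Clopper-Pearson limits as the exact method, true rates of 99% and 1%, and a FAS of the stated size. The missing-rate table also assumes that missingness is unrelated to outcome. The counts that rule out a pass need no assumption about true rates. Failure imputation is not wrong in itself. What is wrong is the unresolved conflict and a power statement that does not apply to the planned analysis.

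**What to change.** 1. Before any 360-day data are analysed, state one missing-data rule for both primary endpoints, identical in Protocol 8.7.2 items (2) and (4) and in SAP 4.2, 5.1.1 and 5.1.2. In doing so, settle the trigger for safety: SAP 4.2 imputes when follow-up within 360 days is incomplete, whereas 5.1.2 imputes when valid data at 360 days are missing.
2. Add to SAP section 4 that its sentence on analysing safety from observed data without imputation does not cover the primary safety endpoint.
3. If failure imputation is kept, remove the claim of 80% power with 20% dropout from Protocol 8.2.1, 8.3 and 8.4. State instead the maximum failures plus missing by FAS size (2 for 118–143, 3 for 144–167) and the power by number or rate missing in the FAS. Replacing the imputation rule is not required.

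The cost is wording in two documents and a less favourable power statement. No extra patients are needed.

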5. ENDPOINTS ANALYSIS

5.1. Primary Endpoints Analysis

For primary efficacy endpoints and safety endpoints, statistical inference will be based on the FAS and PPS. The FAS will serve as the primary dataset for primary endpoint analyses, while the PPS will be the secondary dataset.

5.1.1. Primary efficacy endpoints

Primary efficacy endpoint is effective closure rate at 360-day post operation. Effective closure is defined as no or only a trivial to small residual shunt (based on left-to-right Doppler flow signals with a diameter <5mm) as assessed by TTE or TEE after device implantation.

For the primary efficacy endpoint evaluation, the following hypotheses are tested:

Null hypothesis $H_0: \pi_1 \leq \pi_0$. That is, the Absnow Absorbable Atrial Septal Defect Occluder System fails to meet the design requirement for the 360-day post-operation effective closure rate.

Alternative hypothesis $H_1: \pi_1 > \pi_0$. That is, the Absnow Absorbable Atrial Septal Defect Occluder System meets the design requirement for the 360-day post-operation effective closure rate.

π_1 refers to the expected 360-day post-operation effective closure rate, π_0 refers to the Objective Performance Criteria (OPC) value of 360-day post-operation effective closure rate

Statistical inference will be performed using the exact method to estimate the 95% confidence interval (CI) for the effective closure rate at 360 days post-operation, as well as the P-value for comparison with the predefined performance goal of 94%. If the lower limit of the two-sided 95% CI for the effective closure rate at 360 days exceeds 94%, the null hypothesis will be rejected, and it will be concluded that the Absnow Absorbable Atrial Septal Defect Occluder System meets the

design requirement for the 360-day post-operation effective closure rate. Otherwise, it cannot be concluded that the 360-day effective closure rate meets the predefined performance requirement.

If a subject has missing valid data at 360 days, the subject will be imputed as “ineffective” using the Non-responder Imputation (NRI) method. For analyses based on the PPS, missing data will not be imputed.

5.1.2. Primary safety endpoints

Primary safety endpoint is defined as the rate of common complications during 360 days post operation. For the primary safety endpoint evaluation, the following hypotheses are tested:

Null hypothesis $H_0: \pi_1 \leq \pi_0$. That is, the Absnow Absorbable Atrial Septal Defect Occluder System fails to meet the design requirement for the 360-day common complications rate.

Alternative hypothesis $H_1: \pi_1 > \pi_0$. That is, the Absnow Absorbable Atrial Septal Defect Occluder System meets the design requirement for the 360-day post-operation common complications rate.

π_1 refers to the expected 360-day post-operation common complications rate, π_0 refers to the Objective Performance Criteria (OPC) value of 360-day post-operation common complications rate.

Statistical inference will be performed using the exact method to estimate the 95% confidence interval (CI) for the common complications rate at 360 days post-operation, as well as the P-value for comparison with the predefined performance goal of 6%. If the upper limit of the two-sided 95% CI for the common complications rate at 360 days is less than 6%, the null hypothesis will be rejected, and it will be concluded that the Absnow Absorbable Atrial Septal Defect Occluder System meets the design requirement for the 360-day post-operation common complications rate. Otherwise, it cannot be concluded that the 360-day common complications rate meets the predefined performance requirement.

If a subject has missing valid data at 360 days, the subject will be imputed as “common complications occurred” using the Non-responder Imputation (NRI) method. For analyses based on the PPS, missing data will not be imputed.

The above two clinical endpoints are designated as primary endpoints for analysis in this study. A conclusion that the Absnow™ Bioresorbable Atrial Septal Defect Occlusion System meets the requirements for clinical application will be made only if both primary endpoints achieve the predefined performance criteria. Therefore, no adjustment to the significance level (α) is required.

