7.1 Study design

7.1.1 Study objectives

To evaluate whether the effective closure rate of absorbable ASD closure system at 360-day post operation is not lower than its OPC, and the rate of common complications during 360-day post operation is not higher than its OPC (see 8.2.1 total sample size for details).

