8.5 Qualified/unqualified criteria for clinical trial results

The rate of common complications during 360-day post operation and the effective closure rate at 360-day post operation are calculated. If the upper bound of the 95% CI is less than 6% of the preset target value and the lower bound of the 95% CI is greater than the preset target value of 94%, it can be considered that the safety and efficacy of Absnow™ absorbable ASD closure system meet the criteria. The two indicators are treated according to the co-primary endpoint. It can be concluded that the investigational device meets the clinical application requirements only when both indicators reach the OPC

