4. STATISTICAL CONSIDERATION

For continuous variables, the following will be listed: number of valid cases, mean, standard deviation, median, 25th and 75th percentiles, minimum value, and maximum value. The number of decimal places for the 25th and 75th percentiles, minimum, and maximum values will match the records in the database. The mean and median will retain one more decimal place than the raw data recorded in the database, while the standard deviation will retain two more decimal places than the raw data recorded in the database.

For categorical variables, data will be presented in frequency tables (frequencies and percentages). Percentages will be rounded to one decimal place. When the frequency is zero, only the frequency needs to be listed; the percentage may be omitted to distinguish it from non-

zero values. When calculating percentages, the number of subjects in the specified analysis population will serve as the denominator.

All hypothesis tests employ one-sided tests unless otherwise specified, with a statistical significance level of $\alpha=0.025$. Differences are considered statistically significant when $P<0.025$. All confidence intervals were calculated at the 95% confidence level. P-values were rounded to three decimal places. If $P < 0.001$, the value was output as “<0.001”. If $P > 0.999$, the value was output as “>0.999”.

All analyses in the safety evaluation are based on observed data, without considering data imputation. For table analyses based on the safety analysis set, all subjects receiving at least one treatment with the study device will be included in the analysis. However, for listing analyses, all subjects with safety evaluations will be included, even if they did not receive any trial treatment.

Unless otherwise specified, baseline data shall be defined as the last valid measurement taken before the implant procedure.

When multiple observation data points exist for the same examination at the same follow-up time point, the observation closest in time to the scheduled visit date will be designated as the primary analysis record for the relevant statistical analysis.

Statistical analysis was performed using SAS 9.4[®] software. Subject information and safety databases were exported and stored in SAS XPORT format.

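### SAP 5.1.2 prints the primary safety hypotheses in the wrong direction and does not name the tail of the required one-sided exact P-value

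*SAP*

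**What the plan says.** SAP 5.1.2 takes π₁ as the complications rate and π₀ as its OPC. The null is printed as "\leq \pi_0$. That is, the Absnow Absorbable Atrial Septal Defect Occluder System fails to meet the design requirement for the 360-day common complications rate" and the alternative as "\pi_1 > \pi_0$. That is, the Absnow Absorbable Atrial Septal Defect Occluder System meets the design requirement for the 360-day post-operation common complications rate". These are the same signs that SAP 5.1.1 uses for the effective closure rate.

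The same section then gives the decision rule. The null is rejected on this condition: "If the upper limit of the two-sided 95% CI for the common complications rate at 360 days is less than 6"%. It also asks for a second output from the exact method, "as well as the P-value for comparison with the predefined performance goal of 6"%. SAP section 4 sets the sidedness, "All hypothesis tests employ one-sided tests unless otherwise specified", and calls P < 0.025 significant. Neither section says in words which tail applies to the safety endpoint.

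The protocol has one direction throughout. Section 7.1.1 asks whether "the rate of common complications during 360-day post operation is not higher than its OPC". The SAS code for this endpoint in 8.2.1 tests a null of 0.06 with `sides = L`, whereas the efficacy code uses `sides = U`. Section 8.5 makes success depend on the upper bound: "If the upper bound of the 95% CI is less than 6% of the preset target value".

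**The concern.** For a complications rate, lower is better. The printed signs attach success to a rate above 6% and failure to a rate at or below it. They contradict their own verbal labels, the CI rule a few lines below, and the protocol. The pattern looks like the efficacy hypotheses carried over with only the endpoint name changed.

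This would be purely cosmetic if the CI were the only output. It is not, because a one-sided exact P-value against 6% must be reported as well. A programmer normally takes the tail from the alternative hypothesis, and here that is the upper tail. The table for a co-primary endpoint could then show a CI conclusion and a P-value that contradict each other, in an analysis meant to support a marketing application.

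**Working it through.** **Inputs.** Null rate 0.06 and assumed rate 0.01 (Protocol 8.2.1); one-sided α 0.025 (Protocol 8.3, SAP 4); exact method (SAP 5.1.2); N = 146 (Protocol 8.2.1) and N = 142 (SAP 3.1). The two sample sizes differ between the documents, which is a separate matter, so both are used.

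**1. Direction built into the sample size.** The protocol's 121 comes from a lower-tail test of 6%:

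n = [z₀.₉₇₅ √(p₀q₀) + z₀.₈₀ √(p₁q₁)]² / (p₀ − p₁)²

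= [1.960 × √(0.06 × 0.94) + 0.842 × √(0.01 × 0.99)]² / 0.05² = 120.65, rounded up to 121.

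Power at 121 is 0.802, as printed. The design therefore assumes H₁: π₁ < 6%.

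**2. CI rule against each tail.** For x events in N:

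- lower tail: P(X ≤ x | N, 0.06)
- upper tail, from the printed H₁: P(X ≥ x | N, 0.06)
- upper limit: Clopper-Pearson, 97.5% one-sided

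| N | x | Upper limit | CI rule | Lower-tail P | Upper-tail P |
|---|---|---|---|---|---|
| 142 | 0 | 2.6% | pass | 0.0002 | 1.0000 |
| 142 | 1 | 3.9% | pass | 0.0015 | 0.9998 |
| 142 | 2 | 5.0% | pass | 0.0078 | 0.9985 |
| 142 | 3 | 6.05% | fail | 0.0263 | 0.9922 |
| 142 | 15 | 16.8% | fail | 0.9885 | 0.0239 |
| 146 | 3 | 5.9% | pass | 0.0221 | 0.9936 |
| 146 | 4 | 6.9% | fail | 0.0581 | 0.9779 |
| 146 | 16 | 17.2% | fail | 0.9932 | 0.0147 |

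Over all x from 0 to N:

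- An upper limit below 6% and a lower-tail P below 0.025 select the same counts: 0 to 2 at N = 142, and 0 to 3 at N = 146.
- An upper-tail P below 0.025 selects 15 to 142 and 16 to 146 respectively (from 10.6% and 11.0%).
- The two sets do not overlap.

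**3. Behaviour at the assumed 1% rate, no missing data.** The CI rule passes with probability 0.829 (N = 142) or 0.940 (N = 146). The test in the printed direction would reject with probability about 2.1 × 10⁻¹¹ or 2.5 × 10⁻¹².

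**4. Imputed events.** SAP 4.2 counts a subject as a complication when "safety follow-up data within 360 days is incomplete due to lost to follow-up or other reasons", so x includes imputed cases. As an extreme illustration, take the protocol's 20% maximum dropout (section 8.4) and assume all dropouts are in the FAS: 0.20 × 142 = 28.4, so 28 imputed events. With no observed complication, the upper limit is 27.2% (fail), yet the upper-tail P is 2.5 × 10⁻⁸.

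**The case against.** The strongest reply is that the trial's decision cannot go wrong. SAP 5.1.2 ties rejection of the null to the upper CI limit, the verbal labels of the hypotheses point the right way, and the protocol agrees throughout. The rejection rule stands next to the P-value requirement and uses the same exact method, so a P-value consistent with it can only be the lower tail. A programmer who followed the printed alternative would get P above 0.99 beside a passing CI, which someone would notice. The efficacy section names no tail in words either, so the unnamed tail is a consequence of the sign error and not a second defect.

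Most of this stands, and it limits the point: the intended direction can be inferred and the CI verdict is safe. The dropout illustration adds little, because the CI rule fails there and governs. But the SAP still contradicts itself on the formal hypotheses of a co-primary endpoint. In 5.1.1 the alternative correctly supplies the tail; in 5.1.2 it supplies the wrong one. A statistical analysis plan should settle this before the data are analysed and not rely on someone spotting an odd P-value.

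**Conclusion.** The concern holds. Both inequality signs in SAP 5.1.2 are reversed, and they conflict with the CI rule beside them and with Protocol 7.1.1, 8.2.1 and 8.5. The CI decision, type I error, power and sample size are unaffected. The risk is confined to the reported P-value: taken from the printed alternative, it exceeds 0.99 at every count that passes the CI rule, and it never agrees with that rule on success.

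The result rests on exact binomial calculation and does not depend on whether 142 or 146 is the right sample size. One reservation remains: the signs were read from a PDF by machine, so a reading fault cannot be wholly excluded. It is unlikely, because both signs are reversed consistently and match those in 5.1.1. This should be fixed before analysis, but it does not threaten the trial's conclusion.

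**What to change.** In SAP 5.1.2, print H₀: π₁ ≥ π₀ and H₁: π₁ < π₀, with π₀ = 6%. Add one sentence defining the exact one-sided P-value as P(X ≤ x | n, 0.06), where x is the number of subjects counted as having a complication, including those imputed under SAP 4.2, and n is the number in the analysis set. This P-value agrees with the existing CI rule at every event count.

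The cost is two signs and one sentence. For this point the CI rule, the threshold and the sample size need no change.
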